16.1.1 Effectiveness Variable(s) & data analysis

The Developmental Motor Milestone Checklist variables are described below:

Sitting without support: will be considered as "Sitting without support" the participants who achieves, at each visit, all the two categories below:

- Child sits up straight with the head erect for at least 10 seconds, AND
- Child does not use arms or hands to balance body or support position.

Document: Document path and title

Template No.: RWI_TP_BIOS0013 Revision 2 Reference: RWI_WI_BIOS0015

Hands-and-knees crawling: will be considered as "Hands-and-knees crawling" the participants who achieves, at each visit, all the three categories below:

- Child alternately moves forward or backward on hands and knees, AND
- The stomach does not touch the supporting surface, AND
- There are continuous and consecutive movements, at least 3 in a row.

Standing with assistance: will be considered as "Standing with assistance" the participants who achieves, at each visit, all the three categories below:

- Child stands in upright position on both feet, holding onto a stable object (eg, furniture)
 with both hands without leaning on it, AND
- The body does not touch the stable object, and the legs support most of the body weight, AND
- Child thus stands with assistance for at least 10 seconds.

Walking with assistance: will be considered as "Walking with assistance" the participants who achieves, at each visit, all the four categories below:

- Child is in upright position with the back straight, AND
- Child makes sideways or forward steps by holding onto a stable object (eg, furniture)
 with 1 or both hands, AND
- One leg moves forward while the other supports part of the body weight, AND
- Child takes at least 5 steps in this manner.

Standing alone: will be considered as "Standing alone" the participants who achieves, at each visit, all the three categories below:

- Child stands in upright position on both feet (not on the toes) with the back straight, AND
- The legs support 100% of the child's weight. There is no contact with a person or object,
 AND
- Child stands alone for at least 10 seconds.

Walking alone: will be considered as "Walking alone" the participants who achieves, at each visit, all the three categories below:

Document: Document path and title

Template No.: RWI_TP_BIOS0013 Revision 2 Reference: RWI_WI_BIOS0015

Page 32 of 45

- Child takes at least 5 steps independently in upright position with the back straight, AND
- One leg moves forward while the other supports most of the body weight, AND
- There is no contact with a person or object.

Every milestone will be summarized as the proportion of patients with each criterion met at baseline, week 26, week 52, and week 78. Only descriptive analysis will be performed, and data will be summarized as frequency and percentage.

[figure not shown]
Document: Document path and title

Template No.: RWI_TP_BIOS0013 Revision 2 Reference: RWI_WI_BIOS0015

Page 33 of 45

Statistical Analysis Plan Template

Document: Document path and title

Template No.: RWI_TP_BIOS0013 Revision 2 Reference: RWI_WI_BIOS0015

Page 34 of 45

Document: Document path and title

Template No.: RWI_TP_BIOS0013 Revision 2 Reference: RWI_WI_BIOS0015

Page 35 of 45

Document: Document path and title

Template No.: RWI_TP_BIOS0013 Revision 2 Reference: RWI_WI_BIOS0015

Page 36 of 45

Document: Document path and title

Template No.: RWI_TP_BIOS0013 Revision 2 Reference: RWI_WI_BIOS0015

Page 37 of 45

19. DATA NOT SUMMARIZED OR PRESENTED

The other variables and/or domains not summarized or presented are:

• Comments

These domains and/or variables will not be summarized or presented, but will be available in the clinical study database.

Document: Document path and title

Template No.: RWI_TP_BIOS0013 Revision 2 Reference: RWI_WI_BIOS0015

Page 38 of 45

20. REFERENCES

Not applicable.

Document: Document path and title

Template No.: RWI_TP_BIOS0013 Revision 2 Reference: RWI_WI_BIOS0015

Effective Date: 15Oct2021

-

Page 39 of 45

20.1 APPENDIX 1. Programming Conventions for Outputs

Dates & Times

Depending on data available, dates will take the form dd-mmm-aaaa. Partial data is allowed (see Appendix 2). Time will be represented as hh:mm (24hs format).

To convert a duration or an age from days to months or years, the following conversion factors will be used:

- 1 month = 30.4375 days
- 1 year = 365.25 days

Spelling Format

English US

Listings

All listings will be ordered by the following (unless otherwise indicated in the template):

Center ID

Patient ID

date (where applicable)

Document: Document path and title

Template No.: RWI_TP_BIOS0013 Revision 2 Reference: RWI_WI_BIOS0015

Effective Date: 15Oct2021

Page 40 of 45

20.2 APPENDIX 2. Partial Date Conventions

Appendix table 1. Algorithm for TEAEs and AESIs

START DATE	STOP DATE	ACTION
Known	Known	If start date < study medication (med) start date, then not TEAE If start date >= study medication start date, then
		TEAE
	Partial	If start date < study med start date, then not TEAE
		If start date >= study med start date, then TEAE
	Missing	If start date < study med start date, then not TEAE
		If start date >= study med start date, then TEAE
Partial, but known components show that it cannot be on or after study med start date	Known	Not TEAE
	Partial	Not TEAE
	Missing	Not TEAE
Partial, could be on or	Known	If stop date < study med start date, then not TEAE
after study med start date		If stop date >= study med start date, then TEAE

Document: Document path and title

Template No.: RWI_TP_BIOS0013 Revision 2 Reference: RWI_WI_BIOS0015

Page 41 of 45

START DATE	STOP DATE	ACTION
	Partial	Impute stop date as latest possible date (i.e. last day of month if day unknown or 31st December if day and month are unknown), then: If stop date < study med start date, then not TEAE If stop date >= study med start date, then TEAE
	Missing	Assumed TEAE
Missing	Known	If stop date < study med start date, then not TEAE If stop date >= study med start date, then TEAE
	Partial	Impute stop date as latest possible date (i.e. last day of month if day unknown or 31st December if day and month are unknown), then: If stop date < study med start date, then not TEAE If stop date >= study med start date, then TEAE
	Missing	Assumed TEAE

Document: Document path and title

Template No.: RWI_TP_BIOS0013 Revision 2 Reference: RWI_WI_BIOS0015

Page 42 of 45

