Conditions that were already present at the time of informed consent should be recorded in medical history of the participant.

Adverse events (including lab abnormalities that constitute AEs) should be described using a diagnosis whenever possible, rather than individual underlying signs and symptoms.

Adverse event monitoring should be continued until end of study.

Once an AE is detected, it must be followed until its resolution or until it is judged to be permanent (e.g. continuing at the end of the study), and assessment must be made at each visit (or more frequently, if necessary) of any changes in severity, the suspected relationship to the interventions required to treat it, and the outcome.

Information about adverse drug reactions for the investigational drug can be found in the IB.

Abnormal laboratory values or test results constitute AEs only if they fulfill at least one of the following criteria:

- they induce clinical signs or symptoms
- they are considered clinically significant
- they require therapy

Clinically significant abnormal laboratory values or test results must be identified through a review of values outside of normal ranges/clinically notable ranges, significant changes from baseline or the previous visit, or values which are considered to be non-typical in participant with the underlying disease.

Based on important identified and potential risks associated with OAV101, AESIs are determined and categorized as follows. These will be summarized based on Standardized MedDRA terminology:

- Hepatotoxicity
- Thrombocytopenia
- Cardiac adverse events
- Sensory abnormalities suggestive of ganglionopathy
- Thrombotic microangiopathy

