12.4.2 Statistical model, hypothesis, and method of analysis

No statistical hypothesis testing will be performed.

Treatment-emergent AEs are defined as any event that begins or worsens in severity after infusion of OAV101 through to the last study visit. The incidence of TEAEs will be summarized according to MedDRA as follows: overall by SOC and PT, overall, by SOC, PT and severity, suspected treatment-related AEs by SOC and PT, SAEs by SOC and PT.

Adverse events of special interest (AESI) are defined by the important identified risk and important potential risk as presented in the effective Risk Management Plan (RMP). MedDRA search criteria to retrieve AEs indicative of these risks are updated on a regular basis at the

OAV101 program level. The incidence of treatment emergent AESIs will be summarized. Descriptive summary statistics for the change from baseline in cardiac safety assessments, clinical laboratory measurements, and vital signs will be summarized descriptively by visit/timepoint. Mean, standard deviation, median, minimum, and maximum will be presented. For each applicable visit/timepoint, only participants with a baseline and a measurement for that timepoint will be included in the summary. Categorical cardiac safety assessments, clinical laboratory measurements, and vital signs data will be presented as frequencies and percentages.

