12.4.8 Safety endpoints

For all safety analyses, the Safety set will be used.

The overall observation period will be divided into two mutually exclusive segments:

- 1. Pre-treatment period: from day of participant's informed consent to the day before infusion of OAV101
- 2. On-treatment period: from day of infusion of OAV101 through to the last study visit.

Adverse events

Details of the summary of AEs for the primary endpoint are detailed in Section 12.4.

In addition, separate summaries will be provided for death and other significant TEAEs leading to discontinuation.

All AEs, deaths, and SAEs (including those from the pre-treatment period) will be listed and those collected during the pre-treatment period will be flagged.

Vital signs

Details of the summary of AEs for the primary endpoint are detailed in Section 12.4.

12-lead ECG

Details of the summary of 12-lead ECG (cardiac safety assessment) for the primary endpoint are detailed in Section 12.4

- 1. PR, QRS, QT, QTcF, and RR intervals will be obtained from 12-lead ECGs for each participant during the study. ECG data will be read and interpreted (locally).
- 2. Categorical Analysis of QT/QTc interval data based on the number of participants meeting or exceeding predefined limits in terms of absolute QT/QTc intervals or changes from baseline will be presented.

All ECG data will be summarized by visit/timepoint.

Clinical laboratory results

Details of the summary of clinical laboratory results for the primary endpoint are detailed in Section 12.4.

In addition, shift tables using the low/normal/high/ (low and high) classification will be used to compare baseline to the worst on-treatment value.

Grading of laboratory values will be assigned programmatically as per NCI CTCAE version 4.03. The calculation of CTCAE grades will be based on the observed laboratory values only, clinical assessments will not be taken into account.

CTCAE Grade 0 will be assigned for all non-missing values not graded as 1 or higher. Grade 5 will not be used.

For laboratory tests where grades are not defined by CTCAE version 4.03, results will be categorized as low/normal/high based on laboratory normal ranges.

The following listings/summaries will be generated separately for hematology, and biochemistry tests:

• Listing of all laboratory data with values flagged to show the corresponding CTCAE version 4.03 grades if applicable and the classifications relative to the laboratory normal ranges

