15.1.1 Adverse Events

Adverse Events (AEs) will be coded using MedDRA, Version 25 or later.

Treatment Emergent Adverse Events (TEAEs) are defined as AEs that started or worsened in severity on or after the OAV101 dosing through the last study visit.

Adverse events of special interest (AESI) are defined by the important identified risk an important potential risk as presented in the effective Risk Management Plan (RMP). The AESI will be summarized following the classification presented in Table 2.

Document: Document path and title

Template No.: RWI_TP_BIOS0013 Revision 2 Reference: RWI_WI_BIOS0015

Table 2: Adverse events of special interest classification

AESI	Search methodology (MedDRA version 25.0 or later) [MedDRA
	Code]
Hepatotoxicity	Hepatic disorders SMQ (Broad) [20000005]
Transient thrombocytopenia	Haemorrhages SMQ (Broad) [20000038]
	Haematopoietic thrombocytopenia SMQ (Broad) [20000031]
	HLT: Platelet disorders NEC [10035533]
Thrombotic microangiopathy	PTs:
	Thrombotic microangiopathy [10043645]
	Haemolytic uraemic syndrome [10018932]
	Atypical haemolytic uraemic syndrome [10079840]
Cardiac events	Cardiomyopathy SMQ (Broad) [20000150]
	Ischaemic heart disease SMQ (Broad) [20000043]
	Cardiac arrhythmias SMQ (Broad) [20000049]
	Embolic and thrombotic events SMQ (Broad) [20000081]
	Myocardial infarction SMQ (Broad) [20000047]
	Cardiac failure SMQ (Broad) [20000004]
	Hypertension SMQ (Broad) [20000147]
Sensory Abnormalities	PTs:
Suggestive of Ganglionopathy	Akinaesthesia [10051224]
	Allodynia [10053552]
	Anaesthesia [10002091]
	Anaesthesia dolorosa [10054878]
	Areflexia [10003084]
	Burning feet syndrome [10070237]
	Burning sensation [10006784]
	Central pain syndrome [10064012]

Document: Document path and title

Template No.: RWI_TP_BIOS0013 Revision 2 Reference: RWI_WI_BIOS0015

AESI	Search methodology (MedDRA version 25.0 or later) [MedDRA
	Code]
	Complex regional pain syndrome [10064332]
	Decreased vibratory sense [10067502]
	Discomfort [10013082]
	Dysaesthesia [10013886]
	Formication [10017062]
	Hyperaesthesia [10020568]
	Hyperpathia [10065952]
	Hypoaesthesia [10020937]
	Hyporeflexia [10021089]
	Hyporesponsive to stimuli [10071552]
	Intercostal neuralgia [10049949]
	Joint position sense decreased [10081223]
	Loss of proprioception [10057332]
	Nerve conduction studies abnormal [10029175]
	Nerve stimulation test abnormal [10029192]
	Neuralgia [10029223]
	Neuritis [10029240]
	Neurological symptom [10060860]
	Neuromuscular pain [10074313]

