	Notalgia paraesthetica [10072643]
	Pain [10033371]
	Pain threshold decreased [10066956]
	Paradoxical pain [10067055]
	Paraesthesia [10033775]
	Peripheral nervous system function test abnormal [10034591]
	Peripheral sensorimotor neuropathy [10056673]
	Peripheral sensory neuropathy [10034620]
	Radicular pain [10059604]

Document: Document path and title

Template No.: RWI_TP_BIOS0013 Revision 2 Reference: RWI_WI_BIOS0015

AESI	Search methodology (MedDRA version 25.0 or later) [MedDRA	
	Code]	
	Reflex test abnormal [10068273]	
	Reflexes abnormal [10038254]	
	Reversed hot-cold sensation [10073738]	
	Sensorimotor disorder [10062162]	
	Sensory disturbance [10040026]	
	Sensory ganglionitis [10066196]	
	Sensory integrative dysfunction [10048871]	
	Sensory level abnormal [10061567]	
	Sensory loss [10040030]	
	Skin burning sensation [10054786]	
	Slow response to stimuli [10041045]	
	Synaesthesia [10078814]	
	Temperature perception test decreased [10068015]	
	Tenderness [10043224]	
	Thermoanaesthesia [10068010]	
	Thermohypoaesthesia [10068009]	
	Tinel's sign [10052492]	
	Trichodynia [10079852]	
	Unresponsive to stimuli [10045555]	
	Vibratory sense increased [10068327]	

AESI: Adverse event of special interest; HLT: High Level Terms; PT: Preferred Terms; SMQ: Standardized MedDRA Queries

See Appendix 2 for handling of partial dates for AEs. In the case where it is not possible to define an AE as treatment emergent or not, the AE will be classified by the worst case; i.e. treatment emergent.

Document: Document path and title

Template No.: RWI_TP_BIOS0013 Revision 2 Reference: RWI_WI_BIOS0015

Page 23 of 45

The incidence of TEAEs and AESIs will be summarized. Descriptive summary statistics for the change from baseline in cardiac safety assessments (ECG, Echocardiogram, troponin), clinical laboratory measurements (including hematology and liver function assessments), and vital signs will be summarized descriptively by visit/timepoint. A summary of all laboratorial assessments (including scheduled and unscheduled visits) will be summarized separately. Mean, standard deviation, median, minimum, and maximum will be presented for continuous variables. Categorical data will be presented as frequencies and percentages. For each applicable visit/timepoint, only participants with a baseline and a measurement for that timepoint will be included in the summary.

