15.1.2 All TEAEs and AESI

Incidence of all TEAEs/AESIs and Serious TEAEs/AESIs will be presented by System Organ Class (SOC) and Preferred Term (PT) and also broken down further by maximum severity and relationship to study medication.

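### The SAP's TEAE algorithm has no branch for worsening, so an AE that starts before infusion and worsens afterwards is classed as not treatment-emergent, against the TEAE definition in both documents

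*SAP*

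**What the plan says.** The two definitions agree on the point at issue. Protocol 12.4.2 defines a TEAE as "any event that begins or worsens in severity after infusion of OAV101 through to the last study visit". SAP 15.1.1 refers to "AEs that started or worsened in severity on or after the OAV101 dosing through the last study visit". Each gives two routes to TEAE status: onset after dosing, or worsening after dosing.

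SAP Appendix 2, Appendix table 1, then sets out the classification by start date and stop date. For a fully known start date it says "If start date < study medication (med) start date, then not TEAE", with the same outcome whether the stop date is known, partial or missing. A second group of rows covers a start date described as "Partial, but known components show that it cannot be on or after study med start date"; all three of its rows are also not TEAE.

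SAP 15.1.1 adds a default for unclear cases: "where it is not possible to define an AE as treatment emergent or not, the AE will be classified by the worst case", that is, as treatment-emergent. SAP 4.3 records no change to the analysis from the protocol.

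**The concern.** The table implements the onset route and omits the worsening route. An AE that begins after consent but before infusion, is still present at dosing and then becomes more severe meets both definitions, yet the table returns not TEAE.

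SAP 15.1.2 builds the incidence tables for TEAEs, AESIs and their serious subsets on this status, with breakdowns by maximum severity and by relationship. SAP 15.1 lists these among the primary outcomes. Under SAP 5.1 the two interim analyses, meant as an early safety readout, use the same derivations. The error runs one way: this gap can only lower the counts. In a single-arm descriptive study of about 15 participants, one event can decide whether an AESI category is reported as seen or not seen.

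**Working it through.** **1. Count the branches.** Appendix table 1 crosses 4 start-date classes with 3 stop-date classes, giving 4 × 3 = 12 branches.

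| Start date | Branches | Result for a pre-dose start | Severity tested? |
|---|---|---|---|
| Known | 3 | Not TEAE, whatever the stop date | No |
| Partial, must precede dosing | 3 | Not TEAE, whatever the stop date | No |
| Partial, could be on or after dosing | 3 | Decided by stop date; TEAE if missing | No |
| Missing | 3 | Decided by stop date; TEAE if missing | No |

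The conflict lies in the first two rows: 3 + 3 = 6 branches. The other 6 can return TEAE and are not at issue.

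**2. Run the table and the definition side by side.** These are illustrative records, with dosing on Day 1 and the last visit on Day 547.

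| Start | Worsens | Stop | Table | Definition |
|---|---|---|---|---|
| Day -10 | no | Day -3 | not TEAE | not TEAE |
| Day -10 | no | Day 40 | not TEAE | not TEAE |
| Day -10 | Day 8 | Day 40 | **not TEAE** | **TEAE** |
| Day -10 | Day 8 | missing | **not TEAE** | **TEAE** |
| Day 1 | no | Day 5 | TEAE | TEAE |
| Day 8 | no | Day 20 | TEAE | TEAE |

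They disagree only for pre-dose onset with post-dose worsening.

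**3. Does the worst-case default rescue these events?** No. It applies only where status cannot be defined. With a known pre-dose start the table gives a definite answer.

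**4. Can such events occur?** AE collection starts at consent (Protocol 10.1.1). Screening Visit 1 is at Day -20 with a window of -0/+5, so Day -20 to Day -15. Counted inclusively to Day -1, the onset window is 20 to 15 days. Conditions already present at consent go to medical history, and exclusion criteria 13 to 16 (Protocol 5.2) remove many candidates. An AE that starts on Day -1, after the first corticosteroid dose (Protocol 6.2), is one that can remain. For example, Protocol 4.5 lists raised blood pressure among corticosteroid risks, and the cardiac AESI search in SAP Table 2 includes the hypertension query.

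**5. Is worsening recorded as a new AE?** Neither document says so. Protocol 10.1.1 requires an AE to be followed until it resolves or is judged permanent, and "assessment must be made at each visit (or more frequently, if necessary) of any changes in severity". Protocol 10.1.3 has progression of an SAE reported as follow-up to the original episode. Both point towards one continuing record, though 10.1.3 concerns safety reporting and does not settle CRF practice.

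**6. Size per participant.** With n = 15 from Protocol 12.7.1:

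- The plan's own figure reproduces: 1 - 0.86^15 = 0.896, stated as about 90%. The finding does not depend on it.
- One affected participant with no other event in the category: 1/15 = 6.7 points. Two: 2/15 = 13.3. Three: 3/15 = 20.0.
- If it is the only event in the category, the table shows 0/15 (0%, exact Clopper-Pearson 95% CI 0 to 21.8%) instead of 1/15 (6.7%, 0.2 to 31.9%).

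**The case against.** The strongest reply is that the definition in SAP 15.1.1 governs. Appendix 2 is titled as a set of partial-date conventions, and 15.1.1 sends the reader there only for partial dates. On that reading the known-date rows merely complete the grid for the onset route, and worsening is left to the definition. SAP 4.3, which declares no change from the protocol, is consistent with this. The reading is possible, but it does not explain why a table headed as the TEAE and AESI algorithm gives an unqualified result for fully known dates. A programmer following it would drop the worsened events.

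Second, if sites enter a worsening as a new AE record, the algorithm is correct as it stands. That is true, and it is why a recording rule is offered as an alternative fix. The CRF and its completion guide were not available, and neither document states such a rule. Protocol 10.1.2 does include worsening of a pre-existing condition in its SAE definition, which softens the point for serious events, but it sets no onset-date rule.

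Third, other outputs catch much of this. On listings, Protocol 12.4.8 says "All AEs, deaths, and SAEs (including those from the pre-treatment period) will be listed". Deaths are tabulated under SAP 15.2. Worst post-baseline laboratory grade is reported regardless of baseline (SAP 15.1.6), and the liver and cardiac event summaries in SAP 15.3 and 15.3.1 rest on laboratory thresholds and ECG or echocardiogram findings. This stands: the residual gap is mainly non-laboratory events. It does not correct the incidence tables, and the listings would flag these AEs as pre-treatment.

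Fourth, the 6.7 points would follow from any single misclassified participant, and Protocol 12.7.1 bases the 15 participants on recruitment and drug supply, with the 90% figure only as support. That also stands. The figures show how sensitive the tables are; they do not estimate how often the gap will occur.

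**Conclusion.** The concern holds. Appendix table 1 conflicts with the TEAE definition in both documents for one class of event: onset between consent and infusion, persistence to dosing, and worsening afterwards under the same AE record. Confidence in the conflict is high because it rests on the text alone. The effect on results is unknown: the number of such events is not derivable and may be zero, and there is no effect if worsening is in practice entered as a new record. Where an event does fall in the gap, the error is always an under-count, of 6.7 points per participant with no other event in the category. It should be fixed before the first interim tables are produced, because a primary-endpoint classification rule is wrong as written and correcting it is nearly free.

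**What to change.** Either of two changes is enough.

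1. **Add a worsening branch to Appendix table 1.** If the start date precedes OAV101 dosing and a severity recorded on or after dosing, up to the last study visit, is higher than the last pre-dose severity, class the AE as a TEAE, and as an AESI where the SAP Table 2 search terms match. If worsening cannot be determined, apply the worst-case default already in SAP 15.1.1.
2. **State a recording rule.** Say in the SAP and the CRF completion guide that an increase in severity on or after dosing is entered as a new AE record dated at the worsening. The date algorithm then works unchanged.

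The cost is a SAP wording change and a small programming change, plus a CRF completion note if severity changes are not currently dated. Design, sample size and participant burden are unaffected.
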